#### 11.3.1 Immunosuppressive Medication

##### Maintenance Immunosuppressive Therapy

Maintenance immunosuppressive therapy including tacrolimus, a second agent such as but not limited to MMF or azathioprine, and a systemic corticosteroid such as prednisone as third agent. will be administered according to institutional standards. Dosages, dates of start and stop or change in dosage will be recorded on the respective eCRF.

Systemic tacrolimus doses should not need to be adjusted based on prior experience using aerosolized cyclosporine A. However, systemic tacrolimus doses should be adjusted based upon renal function. Should elevations of creatinine occur during the course of the trial by 30% from baseline at randomization, tacrolimus levels given systemically should be reduced by approximately 30% from baseline and levels should be followed and creatinine monitored according to standard protocols at the discretion of the Investigator.

In the event of renal insufficiency (creatinine > 2.5 mg/dL), the dose of oral tacrolimus may be reduced by 30% and the creatinine should be followed by subsequent monthly blood analyses. Alternatively, a switch from Calcineurin Inhibitor (CNI) to mTOR inhibitors should be considered and will be allowed.

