In addition to the Investigator's own description of the AE, each AE event will be coded by data management according to the MedDRA code list. The verbatim term will be recorded in the eCRF.

Abnormal laboratory test results will be reported as AEs if they are indicative of a clinical condition that meets the criteria for an AE.

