## 15 STATISTICS

This section presents an overview of the planned analyses. Final analyses are not limited to the summaries described herein. The Statistical Analysis Plan (SAP) will provide a detailed description of the planned statistical analyses and data summaries. If circumstances arise during the clinical trial that make these analyses inappropriate or if improved methods become available, the SAP may be revised. If discrepancies exist between the text of the statistical analysis as planned in the protocol and the final SAP, the final SAP will define the planned analysis of record. Reasons for such discrepancies will be described in the final Clinical Study Report (CSR).

Due to serious enrolment problems (see [section 15.5 Sample Size Considerations](#)), it is expected to close this study with fewer than 110 patients originally planned and consequently the study will be underpowered for the assumed effect. Therefore, all planned analyses will be performed and the impact of the reduced sample will be considered. For the same reason, the pre-planned blinded interim analysis for sample size re-estimation will not be performed. The Statistical Analysis Plan (SAP) will provide a detailed description of the statistical analyses.

The primary outcome measure of the trial is the difference in mean FEV1 (mL) change from baseline to Week 48 between the L-CsA plus SoC and SoC alone groups. [CCI](#)

For the purpose of this study, “baseline FEV1” is the mean of the best FEV1 obtained at the Screening Visit and the best FEV1 obtained at the Baseline (randomization) Visit.

For all spirometer-based measurements see [section 15.3](#).

Data will be listed by patient and treatment group.

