#### **15.2.5.3 Laboratory and Other Safety Evaluations**

For clinical safety laboratory test results and vital signs, the numeric values and corresponding changes from baseline will be summarized using descriptive statistics by parameter and time point. In addition to the tables showing the distribution parameters, laboratory measures will be presented in ‘shift tables’ that show the position of all patients relative to the applicable reference range at clinical trial entry, broken down by the position at clinical trial exit. Common Toxicity Criteria (CTC version 5.0) will be applied to abnormal laboratory test results and abnormal vital signs.

Parameters reflecting acute tolerability of IMP (spirometry, cough, or dyspnea) will be summarized.

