9.4 Visit Windows

Following randomization, the visits are scheduled every 4-8 weeks, but the actual times of the visits may deviate from the scheduled times. With spirometry data, consideration needs to be taken to remove the rejected spirometry assessments for analysis before applying the visit windowing.

To allow for any presentation that summarizes values by visit, visit windows will be defined according to the table below. Measurements (both scheduled and unscheduled) will be allocated to visits (and analyzed) as reported in **Table 1**.

Table 1: Visit windows.

Nominal Visit	V1	V2	V3	V4	V5	V6	V7	V8	V9/EoT	V10/EoS
Nominal Week	W0	W4	W8	W12	W16	W24	W32	W40	W48	W52
Nominal Day	1	29	57	85	113	169	225	281	337	365
Time (days) from Randomization***	0	1-42	43-70	71-98	99-140	141-196	197-252	253-308	*309-364 **309-385	*365-385

*Patients who do not consent or participate in BT – L-CsA – 303 – FU (BOSTON-3).

**Patients who consented and participated in BT – L-CsA – 303 – FU (BOSTON-3), and will not have a V10 / EoS.

*** Visit windows are based on [visit date – date of randomization visit] formula for time (days) from randomization.

Data collected after 385 days or 364 days (as applicable, as per the table above) will not be used for analyses but will be included in the listings. If there are two or more measurements assigned to a nominal visit, only the one closest to the scheduled time of the visit will be used in the analysis, unless an additional measurement will be the last measurement during a patient's trial participation (e. g., in case of an unscheduled visit before premature withdrawal), which will always be included into the analysis.

In the case a scheduled visit is performed in the same date of an unscheduled visit, the scheduled visit assessments will be used; in the specific case of spirometries, if the spirometry data is accepted in the scheduled visit, the scheduled visit data will be used, otherwise (if the spirometry in the scheduled visit is rejected) if the spirometry data is accepted in the unscheduled visit, the unscheduled visit data will be used.

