15.5 Clinical Laboratory Data

15.5.1 Hematology and Biochemistry

Clinical laboratory assessments will be performed at each visit by a certified local facility following the routine protocols at each site. As described in the clinical trial protocol (Section 13.1.5), the following clinical laboratory parameters will be reported in the eCRF:

Hematology

- White Blood Cell (WBC) count with differential,
- Red Blood Cell (RBC) count,
- Platelet count,
- Neutrophils,
- Lymphocytes,
- Monocytes,
- Eosinophils,
- Basophils,
- Neutrophils Absolute Count,
- Lymphocytes absolute counts,
- Eosinophils absolute count,
- Basophils absolute count,

- Monocyte absolute count.

Biochemistry

- Alkaline phosphatase (AP),
- Alanine aminotransferase (ALT),
- Aspartate aminotransferase (AST),
- Gamma Glutamyl Transferase (γ -GT),
- Blood urea nitrogen (BUN),
- Serum bilirubin,
- Serum creatinine,
- Sodium,
- Potassium,
- Chloride,
- Bicarbonate,
- Calcium,
- Magnesium.

Descriptive statistics of observed values and changes from baseline will be presented by visit and treatment group. The summaries described in this section will be presented relative to baseline, defined as the most recent, non-missing result on or before the date of randomization. No imputation for missing data will be performed.

All clinical laboratory data reported in the eCRF will be presented in by-patient listings.

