15.6 Renal Function

In addition to the summarization of serum creatinine as described in previous section, renal dysfunction will be further listed and summarized by treatment group based upon the classification of AEs with the following PTs (see protocol section 13.1.5.4, Table 7 and SAP section 16):

- Blood Creatinine Increased,
- Renal Impairment,
- Renal Failure,
- Acute kidney injury,
- Azotaemia,
- Chronic kidney disease,
- Proteinuria,
- Renal disorder.

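### The readable SAP does not carry forward the protocol's laboratory shift tables and CTC v5.0 grading, which leaves serum creatinine without a readable by-arm laboratory count of patients becoming abnormal

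*SAP*

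**What the plan says.** Protocol 15.2.5.3 plans summary statistics for laboratory data and two further outputs. The first is a shift table showing each patient's position "relative to the applicable reference range at clinical trial entry, broken down by the position at clinical trial exit". The second is toxicity grading: "Common Toxicity Criteria (CTC version 5.0) will be applied to abnormal laboratory test results and abnormal vital signs".

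SAP 15.5.1, which covers serum creatinine, says that "Descriptive statistics of observed values and changes from baseline will be presented by visit and treatment group". It adds by-patient listings. SAP 8.1 defines the descriptive statistics as n, mean, SD, median, quartiles, minimum and maximum. SAP 15.6 adds an adverse event output: "renal dysfunction will be further listed and summarized by treatment group based upon the classification of AEs with the following PTs", followed by eight preferred terms.

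Protocol section 15 settles which document governs: "the final SAP will define the planned analysis of record". SAP section 16 lists changes from the protocol. Its readable bullets record the added renal preferred terms but say nothing about shift tables or CTC grading. Several of its bullets are redacted.

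**The concern.** Renal function is a named safety endpoint in both documents, and Protocol 13.1.5.4 singles out serum creatinine as its key parameter. The trial adds an inhaled calcineurin inhibitor to systemic tacrolimus. Protocol 7.1.3 and 7.1.4 report no increased nephrotoxicity so far. The direct check of that statement is how many patients in each arm became abnormal, and how badly.

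The shift table and the CTC grading are the two protocol outputs that would give such counts from laboratory values. If the SAP is followed as its readable text stands, neither is produced. A reader of the study report would then have by-visit summaries, patient listings and an adverse event table from which to judge renal safety.

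**Working it through.** **1. The two plans side by side**

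| Laboratory output | Protocol 15.2.5.3 | Readable SAP 15.5.1 |
|---|---|---|
| Descriptive statistics by time point | yes | yes |
| Shift table, entry to exit | yes | not mentioned |
| CTC v5.0 grading | yes | not mentioned |
| By-patient listings | not in this section | yes |

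The protocol sentence on CTC also covers vital signs. SAP 15.7 likewise names only descriptive statistics and listings.

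**2. Can the renal adverse event table stand in?** Only indirectly. An abnormal creatinine enters it by investigator judgement: "Abnormal laboratory test results will be reported as AEs if they are indicative of a clinical condition that meets the criteria for an AE". In Protocol Table 7 the preferred term *Renal impairment* takes in conditions from a sustained rise needing no treatment to creatinine stably above 2.5 mg/dL. The severity and seriousness tables in SAP 15.3 separate these in part.

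**3. Can the by-visit statistics stand in?** Inputs: 62 randomized (SAP 8.2); 31 per arm, assuming an equal split and no missing values at the visit.
- Third quartile position: 0.75 × 31 = 23.25, so it is the 24th ordered value.
- If the maximum is above a cut-off and the third quartile is below it, at least 1 patient and at most 31 − 24 = 7 are above: 1/31 = 3.2% to 7/31 = 22.6%.
- If the maximum is below the cut-off, the count among the values used at that visit is zero. The statistics are informative in that case.
- The mean adds little. If three patients each rose by 1.3 mg/dL (an illustrative figure), the arm mean would move by 3 × 1.3 / 31 = 0.13 mg/dL.
- Visit rows cannot be linked, so patients cannot be counted over the whole trial.

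**4. Which values reach the by-visit table?** SAP 9.4 allocates scheduled and unscheduled measurements to windows. Where a window holds several, "only the one closest to the scheduled time of the visit will be used in the analysis", unless another is the patient's last. An unscheduled peak can therefore be missing from the visit maximum, although it stays in the listing if it was entered in the eCRF.

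**5. Would the protocol's shift table be enough?** Not for a transient rise. Protocol 11.3.1 begins "Should elevations of creatinine occur during the course of the trial by 30% from baseline at randomization" and goes on to advise lowering tacrolimus by roughly 30%, with monitoring at the investigator's discretion. A creatinine that rises and then falls after such a change may show no shift between entry and exit. Grading by the worst post-baseline value would capture it, if the value was recorded.

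**6. Can a 30% rise be read from changes in mg/dL?** The threshold is 0.3 × baseline. At illustrative baselines of 1.0, 1.5 and 2.0 mg/dL it is 0.30, 0.45 and 0.60. A change of +0.5 reaches 30% only at baselines up to 0.5 / 0.3 = 1.67. A table of absolute changes therefore does not give this count.

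**7. How precise would a count be?** Three of 31 is 9.7%, with an exact 95% interval of 2.0% to 25.8%.

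**The case against.** The strongest objection is that silence is not removal. No readable SAP text says the outputs are dropped, several section 16 bullets are redacted, and SAP 9.1 refers to table shells that are not among the documents. Protocol section 15 also assigns the explanation of protocol–SAP discrepancies to the study report, so a missing section 16 entry is not in itself a breach. This stands. A reader might infer that the sponsor deliberately and silently discarded the outputs, and the documents do not support that.

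A second objection is that much is already covered: by-arm maxima and quartiles, by-arm renal adverse event counts, severity and seriousness tables, full listings, calcineurin inhibitor doses and troughs by arm, and DMC review of creatinine. With 62 patients, the listings can be counted by hand. This limits the consequence. It does not replace a prespecified by-arm output, because a hand count made after the data are seen leaves the cut-off and the choice of values open.

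A third objection is that neither document plans a count at 30% or at 2.5 mg/dL. Those figures guide tacrolimus dosing and do not define a safety endpoint. This is correct. A reader might infer that the SAP omits a promised threshold table; it does not. Such a table would be an addition.

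Finally, the documents do not assure that blood results obtained between visits are entered in the eCRF. Protocol 13.1.5 covers laboratory tests at visits and 14.2.7 covers measures at unscheduled visits. Any new table would be limited to what was recorded.

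**Conclusion.** The point holds on the readable text. Two laboratory outputs planned in the protocol are absent from the readable SAP, which is the analysis of record. No other readable output gives a by-arm laboratory count of patients whose creatinine became abnormal. Confidence is medium because of the redactions and the unseen shells.

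The gap is in prespecified reporting. Scheduled creatinine values are collected and listed, and the efficacy analyses are unaffected. A reader might also infer that renal safety goes unreported by arm, but the by-visit statistics and the renal adverse event table rule that out. The loss is the 1-to-7-of-31 ambiguity shown above at any such visit, and the inability to count patients across visits. Those figures assume an equal split and complete data at the visit. The baselines and the size of rise used in the working are illustrative, because the documents give no creatinine distribution. SAP 15.1 plans no safety inference, so any restored counts would be descriptive.

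**What to change.** Restore the laboratory shift tables and CTC v5.0 grading in SAP 15.5.1. State that grading uses each patient's worst post-baseline value, including unscheduled values recorded in the eCRF. If the outputs are in fact dropped, say so in section 16 with the reason. If they are already in the table shells, one sentence in 15.5.1 pointing there is enough.

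As an optional addition that the protocol does not itself plan, put one by-arm table in SAP 15.6. It would give the number and percentage of patients with any recorded post-baseline creatinine (a) at least 30% above baseline and (b) above 2.5 mg/dL. These are the dose-management thresholds in Protocol 11.3.1. Patients above 2.5 mg/dL at screening are excluded, so (b) would be almost entirely new crossings. A footnote can flag anyone who was already above it at baseline, since baseline may be up to four weeks after screening. Keep the preferred term table.

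The cost is some SAP wording and a few descriptive tables with small counts. No new data collection is required, but the tables can show only values entered in the eCRF.

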15.5.2 Blood Sampling CNI/mTOR Inhibitors

A whole blood sample for the determination of blood sampling calcineurin inhibitor/mammalian target of rapamycin (CNI/mTOR) inhibitors, where for CNI, cyclosporine A and/or tacrolimus trough level will be collected at each visit. In patients allocated to L-CsA plus SoC, the sample should be collected 60 min before L-CsA inhalation. Blood samples will be evaluated by the local laboratories associated with each site. The summaries described in this section will be presented relative to baseline, defined as the most recent, non-missing result on or before the date of randomization. No imputation for missing data will be performed.

All CNI/mTOR data reported in the eCRF will be presented in by-patient listings. Descriptive statistics of observed values and changes from baseline will be presented by visit and treatment group.

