#### 7.1.3 Nonclinical Data

For systemic administration of CsA, the nonclinical pharmacologic, pharmacokinetic, and toxicity profiles of systemic CsA are well established [UK SmPC Ciclosporin A CCI [REDACTED]).

For aerosolized administration of L-CsA, additional nonclinical studies have been conducted with L-CsA. Importantly, L-CsA inhibited T-cell proliferation in stimulated human peripheral blood

mononuclear cells. Across 3 nonclinical toxicology studies in rats, aerosolized L-CsA given as 4-day, 6-week, and 26-week repeated applications of up to 2.6 mg/kg/day, no dose-limiting toxicity occurred. The no-observed-adverse-effect-level (NOAEL) is considered to be 2.0 mg/kg/day via inhalation for chronic application based on the maximum dosage achieved in the 26-week inhalation study in rats.

Nonclinical and clinical data to date with L-CsA show negligible increase in serum levels of calcineurin inhibitors and do not show an increased risk of nephrotoxicity, respiratory infections, or malignancies.

Additional information can be found in the IB.

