#### **11.3.4 Other Medication**

All concurrent treatment or medications given within 30 days prior to Randomization and until Visit 10/EoS, will be recorded in the eCRF.

The use of any inhaled formulation of Cyclosporine A other than the IMP is strictly prohibited during the complete clinical trial period. Topical formulations (e.g., eye drops) containing CsA are allowed. Patients should not receive systemic Cyclosporine A at any time during Screening and Randomization. If medically indicated after Randomization, the treating physician can exchange Tacrolimus for systemic Cyclosporine A.

[figure not shown]
[figure not shown]
[figure not shown]
[figure not shown]
[figure not shown]
All inhaled medications, except investigational inhaled medications, are permissible during the trial and should be administered in the following order: inhaled bronchodilators, inhaled corticosteroids, inhaled antifungals/antibiotics, and then inhaled L-CsA. Spirometry must be performed without the use of bronchodilators (see [Section 12.1.1](#)) and preferably before but at least 2 hours after the last administration of inhaled antifungals/antibiotics.

To standardize spirometry across the two treatment arms, patients should not use short-acting bronchodilators (e.g., albuterol) within 2 hours prior to spirometry. Patients on scheduled Long-Acting Beta Agonists (LABAs) or Long-Acting Muscarinic Antagonists (LAMAs) should ideally have spirometry done at the same time of day following their scheduled dose. Patients have to note their use and timing of bronchodilators carefully.

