#### **13.1.5.2 Cyclosporine A and Tacrolimus Whole Blood Trough Levels**

A whole blood sample for the determination of cyclosporine A and/or tacrolimus trough level will be collected at each visit. In patients allocated to L-CsA inhalation, the sample should be collected within 60 minutes before inhalation. The mean cyclosporine A and/or tacrolimus trough level will be compared across treatment groups. Blood samples will be evaluated by the local laboratories.

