EQ-5D-5L			X			

NOTE: The Screening phase (time between screening and randomization visit) last from one day to up to 4 weeks.

 Conduct prior to any screening activities.

 Not more than 7 days prior to Randomization. Urine pregnancy test is allowed at Visit 1 only. Austria only: Urine pregnancy tests will be performed every month according to local law (Visits 5 through 9).

 Including body weight, height (Screening Visit only), cardiovascular, respiratory, nervous, gastrointestinal, hepatic, renal, dermatological, musculoskeletal, extremities, eyes, ears, nose, throat, and lymphatic.

 Including systolic and diastolic blood pressure (sitting, after 5 minutes of rest), pulse rate (sitting, after 5 minutes of rest), body temperature (the same method should be used for each patient and throughout the clinical trial), and respiratory rate.

 At all visits, spirometry will be performed on the CCI and on the CCI as per Section 12.1.1. At the Baseline Visit (V1), serial spirometry is to be performed prior to Randomization (CCI and CCI; CCI only), and (CCI; CCI only) after completion of L-CsA dose (or after Randomization to SoC). Remote visits will be performed using the CCI device only. Visit 10 spirometry will be performed in those patients not rolling over to Boston 3 on the CCI only.

 Only in patients randomized to receive L-CsA treatment.

[figure not shown]
 within 60 minutes prior to next CNI administration. Blood levels of mTor inhibitors will be taken only if applicable, i.e., if patient is treated with mTor inhibitors.

 ±3 days of the Visit date.

 If a DSA test performed within 4 weeks before screening is available, a further DSA test at screening visit will not be mandatory.

 Laboratory tests at V1 are not mandatory in case laboratory tests at screening visit have been performed within 2 weeks from V1.

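### Blood cyclosporine is summarized by arm without separating samples taken on systemic cyclosporine, so the arm means can mask, reverse or exaggerate any inhaled contribution

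*SAP*

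**What the plan says.** Systemic cyclosporine is excluded at entry. Protocol 11.3.4 states: "Patients should not receive systemic Cyclosporine A at any time during Screening and Randomization". It then allows the drug later, without restriction by arm: "If medically indicated after Randomization, the treating physician can exchange Tacrolimus for systemic Cyclosporine A".

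Protocol 13.1.5.2 has a blood sample taken at each visit and sets out the comparison: "The mean cyclosporine A and/or tacrolimus trough level will be compared across treatment groups". SAP 15.5.2 implements this with "Descriptive statistics of observed values and changes from baseline will be presented by visit and treatment group", and adds "All CNI/mTOR data reported in the eCRF will be presented in by-patient listings" and "No imputation for missing data will be performed". Neither section excludes, flags or stratifies samples taken on systemic cyclosporine. Neither says whether a patient on tacrolimus alone has cyclosporine measured, or how a result below quantification enters the table.

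Three passages time the sample. For L-CsA patients, Protocol 13.1.5.2 allows the hour before inhalation and SAP 15.5.2 says 60 minutes before inhalation. Footnote 7 of the Protocol's Schedule of Activities says "within 60 minutes prior to next CNI administration".

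The data needed for a split exist. Protocol 11.3.1 requires doses and start, stop and change dates of maintenance immunosuppressants to be recorded. SAP 12.1 identifies tacrolimus and cyclosporine A by name, although it groups them in one class and does not link them to 15.5.2.

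**The concern.** After randomization, blood cyclosporine has two permitted sources of consequence: inhaled L-CsA, in one arm only, and a switch to systemic cyclosporine, in either arm. A summary by arm over all samples adds them together. In the SoC arm, any material cyclosporine level comes from a switched patient. In the L-CsA arm, a few therapeutic levels sit among values that reflect inhalation alone.

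The protocol leans on low systemic exposure in several places. Section 7.1.3 says: "Nonclinical and clinical data to date with L-CsA show negligible increase in serum levels of calcineurin inhibitors". Section 8.2 refers to minimal absorption into the circulation, and Section 9.2 uses the absence of added systemic burden when arguing that open-label bias is low. A randomized comparison with SoC could add direct evidence on that premise. A table that mixes the two sources adds little, and could mislead a reader who looks only at the means.

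**Working it through.** The documents state no trough level, absorption figure or switch count, so there is no planned figure to reproduce. What can be checked is how sensitive the planned arm means are to switching.

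**Inputs**
- 62 patients randomized (SAP 8.2) at 1:1 (SAP 7.2), taken as 31 per arm. The actual arm sizes are not given.
- I, the trough contribution of inhaled L-CsA: assumed, 2 to 20 ng/mL.
- S, the trough on systemic cyclosporine: assumed, 80 to 250 ng/mL.
- kL and kC, the numbers switched in the L-CsA and SoC arms: unknown, so varied.

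**Case 1: unswitched SoC patients enter as zero**

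L-CsA mean = I + kL × S/31, and SoC mean = kC × S/31.

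Difference = I − (kC − kL) × S/31. It changes sign when kC − kL > 31 × I/S.

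With I = 5 and S = 150 (ng/mL):

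| kC | kL | SoC mean | L-CsA mean | Difference |
|---|---|---|---|---|
| 0 | 0 | 0.0 | 5.0 | +5.0 |
| 1 | 0 | 150/31 = 4.8 | 5.0 | +0.2 |
| 2 | 0 | 300/31 = 9.7 | 5.0 | −4.7 |
| 2 | 2 | 9.7 | 5 + 300/31 = 14.7 | +5.0 |
| 0 | 2 | 0.0 | 14.7 | +14.7 |

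Over the assumed ranges, the smallest threshold is 31 × 2/250 = 0.25, so a net excess of 1 switched SoC patient reverses the means. The largest is 31 × 20/80 = 7.75, so 8 are needed.

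The medians stay at 0 (SoC) and 5 (L-CsA) in every row of the table.

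**Case 2: unswitched SoC patients have no cyclosporine result**

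Under no imputation they drop out, and the SoC row consists only of switched patients. With I = 5, S = 150 and one SoC switch, the table shows a SoC mean and median of 150 (n = 1) against an L-CsA mean of 5.0. Only the small n warns the reader.

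**With the split**

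Among samples without concurrent systemic cyclosporine, the L-CsA mean is 5 in every row above. The SoC value is 0 in Case 1, which restores +5. In Case 2 there is no SoC value, and the table says so openly.

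**Tacrolimus**

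A patient who has stopped tacrolimus lowers the arm mean only if an off-drug value is recorded. If no result is entered, the patient drops out and the mean already describes patients on the drug. The SAP does not say which applies.

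**The case against.** The strongest reply is that the planned output is more than a mean. SAP 8.1 requires n, median, quartiles, minimum and maximum. Suppose I = 10 and S = 150, with one switch in the L-CsA arm and four in SoC. Under zero scoring the means are (30 × 10 + 160)/31 = 14.8 and 600/31 = 19.4, a difference of −4.5. The medians and both quartiles are still 10 against 0, and the maxima of 160 and 150 point to the switched patients. SAP 15.5.2 lists every level by patient and SAP 12.1 lists every basic immunosuppressant, so switched patients could be traced among 62. This stands and limits the harm. It does not remove it: the reader must join two listings by date, and in Case 2 the median is no better than the mean.

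A reader might infer that the table is intended to demonstrate absorption of inhaled L-CsA and fails at that task. The documents do not support this. No passage gives the table that purpose; it reads as routine monitoring of calcineurin and mTOR inhibitors, and the nearest statement of aim is a general remark on monitoring cyclosporine levels in Appendix II. The statements in Protocol 7.1.3 and 9.2 report earlier evidence. Renal safety is assessed separately through creatinine (SAP 15.5.1) and renal adverse events (SAP 15.6), and SAP 15.1 plans no safety inference.

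A reader might also infer that switching would systematically conceal absorption. That needs an excess of switches in SoC, for which there is no evidence. Under zero scoring, equal switching leaves the difference unchanged, and an excess in the L-CsA arm inflates it.

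Finally, the timing passages need not conflict. One sample can precede both the inhalation and the next oral dose by less than an hour. They do use different reference points, so the wording should be reconciled.

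**Conclusion.** The gap is real and modest. The plan permits a switch to systemic cyclosporine in either arm and then averages cyclosporine by arm as if no one had switched. If switches occur, the means can mask, reverse or exaggerate the between-arm difference, depending on which arm has more of them and on whether unswitched SoC patients have a result.

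Under the assumed ranges, a net excess of 1 to 8 switched SoC patients out of 31 reverses the means when non-users count as zero. Those figures rest on assumed concentrations, assumed switch counts and arms of 31; they show sensitivity and do not predict what happened. If nobody switched, the planned table is unaffected on this point. The table is descriptive, and the primary endpoint and its analysis are untouched.

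**What to change.** In SAP 15.5.2:
- Flag each sample by concurrent systemic cyclosporine, comparing the sample date with the concomitant-medication start and stop dates.
- Present cyclosporine by visit and arm separately for samples with and without concurrent systemic cyclosporine. Give the number measured and the number below quantification in each cell, and state how the latter enter the mean. Counts matter because the assays are local and their limits may differ.
- Restrict tacrolimus summaries to samples taken while the patient is on tacrolimus.

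Reconcile the sampling-time wording in Protocol 13.1.5.2, footnote 7 of the Schedule of Activities and SAP 15.5.2.

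The cost is a few lines of SAP text and one derived flag, with no new data collection. The downside is slightly smaller denominators at late visits.
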